Protocol title:

Feasibility of using daily Humidified Nasal High-flow with Oxygen during Sleep and/or Daytime in Hypercapnic COPD patients following recent (< 12 wks.) hospitalization for AECOPD for 90 days

NCT03221387

Date: 10/06/2017

1) Abstract of the study

Humidified Nasal High-flow with Oxygen (HNHF-O2) therapy has been reported to have acute beneficial effects in patients with hypoxemic respiratory failure. HNHF-O2 may be beneficial in patients with COPD and chronic impairments in gas exchange, both hypoxemia as well as hypercapnia. HNHF-O2 may decrease work of breathing, reduce dyspnea, improve airway humidification, and potentially stabilize or reduce carbon dioxide levels. However, there is limited data showing the chronic effects of HNHF-O2 in patients with hypercapnic respiratory failure, specifically those discharged to home following hospitalization for an acute exacerbation. Data that demonstrates that HNHF-O2 is well tolerated, and stabilizes or improves gas exchange long term in patients with COPD is lacking. Similarly, data that demonstrates that this therapeutic regimen is feasible to provide to patients in the home environment are lacking. This is an open-labeled pilot study of thirty patients to determine the safety and feasibility of using the device in the outpatient management of patients with COPD.

2) Protocol Title

Feasibility of using daily Humidified Nasal High-flow with Oxygen during Sleep and/or Daytime in Hypercapnic COPD patients following recent (< 12 wks.) hospitalization for AECOPD for 90 days

3) IRB Review History

Not applicable

4) Investigator

[name]

5) Objectives

To assess the feasibility of using daily home HNHF-O2 during sleep and/or daytime in hypercapnic COPD patients following recent (< 12 weeks) hospitalization for AECOPD for 90 days.

6) Background

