We treat an average of 16,000 outpatients a year; over 50% of these patients carry a diagnosis of advanced lung disease, including COPD, IPF, pulmonary hypertension, and bronchiectasis. We are a major referral center for lung volume reduction surgery.

All physicians, nurses and ancillary staff members will be instructed in the details of this study.

9) Prior Approvals

Not applicable.

10) Study Design

a) Recruitment Methods

Thirty patients hospitalized for acute exacerbation of COPD \leq the last 12 weeks will be enrolled into the study. Subjects will be recruited from the Temple Lung Center clinical practices in Philadelphia and Oaks, PA.

Potential subjects will be recruited during scheduled office visits to the Temple Lung Center offices in Philadelphia and in Oaks, PA. Many of these patients will be those who have been referred to Temple. We will also contact pulmonology practices in the tri-state area through direct mailings and our monthly research fax blast. The Temple Lung Center also maintains an IRB-approved registry of patients who have agreed to be contacted to discuss participation in clinical research trials.

Describe materials that will be used to recruit subjects. Include copies of these documents with the application. – Not applicable

Subjects will receive compensation in the form of a \$25 gift card for each completed visit during their participation in this study.

b) Inclusion and Exclusion Criteria

Consecutive patients \geq 40 years of age or older who are admitted to the hospital for an acute exacerbation of COPD within the past 12 weeks. Patients will have COPD as the primary diagnosis and have smoked > 10 pack years. Patients should be receiving supplemental oxygen as part of their usual clinical care.

Patients must be willing to give informed consent and be willing to participate in measurement of ABGs, brief history and physical examination and answer questionnaires regarding daily use of HNHF-O2 therapy. Women who are pregnant are excluded from this research. Women of childbearing potential will have a urine pregnancy test to ensure that they are not pregnant.

The main exclusion criteria are upper airway or nasal problems that prohibit the use of high flow oxygen and patients with any of the following will be excluded:

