current use (\leq 4 weeks of study entry) of any PAP-therapy (e.g., CPAP or NPPV); sleep apnea as follows: STOPBang scores \geq 5 or STOPBang score \geq 2 plus BMI $>$ 35 kg/m²; or Berlin questionnaire scores suggesting high likelihood of sleep apnea with increased risk of sleep-related accident (e.g., occupation as a commercial driver or pilot); or excessive daytime sleepiness (i.e., either of High (>15) score on the Epworth Sleepiness Scale or “fall asleep” accident or “near miss” accident in prior 12 months).

c) Local Number of Subjects

Thirty subjects will be accrued locally for this study.

We expect few screen failures.

d) Study-Wide Number of Subjects

If this is a multicenter study, indicate the total number of subjects to be accrued across all sites. – Not applicable.

e) Study Timelines

- Subjects will be followed for 90 days with regular telephone follow-up and clinic visits throughout.
- Subjects will be enrolled over a period of 12 months.
- The investigators will complete the data analysis approximately 18 months after the first subject is enrolled.

f) Study Endpoints

The primary endpoints of this study are the feasibility of oxygen therapy by HNHF-O2 at home over a 90-day period in terms of tolerance and hours of use. Descriptive statistics will be used to characterize the patient population in terms of demographic factors and severity of airflow obstruction. Changes in PaO₂, PaCO₂ and pH across the days will be done by analysis of variance. The effect of baseline PaCO₂ on change in PaCO₂ with HNHF-O2 therapy will be analyzed as an independent effect on change in PaCO₂ levels with HNHF-O2. Changes in respiratory rate, heart rate, blood pressure accessory muscle use will also be assessed by analysis of variance. Patient tolerance and side effects will also be measured across days of use per patient and across days in all patients as group trends. Hours of use per device log and per patient diary will be independently analyzed and compared to one another. The impact on change in exacerbation frequency and severity will be analyzed. Changes in spirometry, 6MWD, GOLD grade and class and BODE scores prior to and after 90 days of HNHF-O2 will be analyzed.

g) Procedures Involved in the Human Research

[figure not shown]
An overview of the study is provided in the figure below.

Outpatient HNHF-O2 Protocol

Version 3.0

10/06/2017

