At baseline, patients will have measurement of vital signs (heart rate, respiratory rate and blood pressure), dyspnea (modified Borg score, mMRC) arterial blood gas after 5 minutes of inspiring supplemental oxygen to keep $\text{SaO}_2 > 90\%$, and use of accessory muscles of ventilation. Patients will have spirometry performed pre-and post-bronchodilator administration. Patients will have assessment of their current respiratory health by completing CAT, mMRC and SGRQ questionnaires. A detailed history of their exacerbation frequency and severity will be obtained. Patients will perform a 6-minute walk test. Patients GOLD grade and group will be classified and patients BODE scores will be calculated.

Patients will be queried regarding the presence and magnitude of complaints of cough and sputum production by using a daily electronic diary for a 2-week period of run in. After the 2-week run-in period the patient will be scheduled to return to initiate HFNC with oxygen therapy.

Electronic daily diary of respiratory symptoms.

- ❖ Breathlessness (Modified Borg Scale)
- ❖ Sputum Quantity, Color, and Consistency
- ❖ Peak Flow Measurements
- ❖ Presence of Temperature Over 100°F
- ❖ Presence of Any Cough, Wheeze, Sore Throat or Nasal Congestion

Outpatient HNHF-O2 Protocol

Version 3.0

10/06/2017

Patients will be seen in clinic and instructed in the use of HNHF-O2 and its proposed benefits. The necessity of compliance and adherence to the treatment plan will be emphasized.

Following the outpatient clinic visit, patients will be set up at home using an established home vendor for respiratory equipment. Patients will continue to report their daily respiratory symptoms via the electronic diary.

Post placement on optimal dose of HNHF-O2 therapy, subjects will be called the next day to determine if there were any problems.

Patients will report to clinic at baseline and then 7 ± 2 , 28 ± 5 , 49 ± 5 , and 70 ± 5 days for the following assessment:

- Measurements of vital signs (heart rate, respiratory rate and blood pressure)
- Respiratory patient-discomfort and dyspnea assessed using an unmarked 100 mm visual analogic scale from “no discomfort” to “maximal imaginable discomfort”
- Likert scale model indicating marked improvement (+2), slight improvement (+1), no change (0), slight deterioration (-1) and marked deterioration (-2)

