- Side effects related to high flow nasal administration: nasal dryness, epistaxis, nasal crusting, eye discomfort, pressure discomfort, increase rhinitis, decreased smell, post nasal drip, hoarseness
- Hours of daily use of HNHF-O2 therapy
- Daily record keeping of daily diary review

At day 90 ± 2 the following will be measured:

- Measurements of vital signs (heart rate, respiratory rate and blood pressure)
- Respiratory patient-discomfort and dyspnea assessed using an unmarked 100 mm visual analogic scale from “no discomfort” to “maximal imaginable discomfort”
- Likert scale model indicating marked improvement (+2), slight improvement (+1), no change (0), slight deterioration (-1) and marked deterioration (-2)
- Side effects related to high flow nasal administration: nasal dryness, epistaxis, nasal crusting, eye discomfort, pressure discomfort, increase rhinitis, decreased smell, post nasal drip, hoarseness
- Hours of daily use of HNHF-O2 therapy
- Daily record keeping of daily diary review
- Arterial blood gas on room air after the participant has been off the Airvo Device for 20 minutes.
- Pre-and post-bronchodilator spirometry

Outpatient HNHF-O2 Protocol

Version 3.0

10/06/2017

- CAT, SGRQ
- 6 Minute walk test
- GOLD grade and group will be classified
- BODE scores will be calculated.

Application of HNHF-O2 therapy. During HNHF-O2, oxygen will be passed through a heated humidifier (myAIRVO 2, Fisher and Paykel Healthcare) and applied continuously through large-bore binasal prongs, with a gas flow rate of 20-35 liters per minute (or as high as tolerated). Temperature will be adjusted based on patient's comfort and range from 34-37 degrees based on prior experience. The fraction of oxygen in the gas flowing in the system will be adjusted to maintain an SpO2 of 90% or more. High-flow oxygen will be applied at the highest tolerated flow up to 35 lpm at home. Meter time and patient's log of hours of daily use will be measured and compared.

Hypercapnic COPD patients are encouraged to use supplemental oxygen therapy on a continuous basis. The use of the humidified nasal high-flow device in this protocol is not expected to change the total number of hours that the patient receives supplemental oxygen; however it will change the manner in which the oxygen is delivered. Patients will be encouraged to use the device for oxygen delivery as many hours per day as possible.

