The primary endpoints of this study are the feasibility of oxygen therapy by HNHF-O2 at home over a 90-day period in terms of tolerance and hours of use. Descriptive statistics will be used to characterize the patient population in terms of demographic factors and severity of airflow obstruction. Changes in PaO₂, PaCO₂ and pH across the days will be done by analysis of variance. The effect of baseline PaCO₂ on change in PaCO₂ with HNHF-O2 therapy will be analyzed as an independent effect on change in PaCO₂ levels with HNHF-O2. Changes in respiratory rate, heart rate, blood pressure accessory muscle use will also be assessed by analysis of variance. Patient tolerance and side effects will also be measured across days of use per patient and across days in all patients as group trends. Hours of use per device log and per patient diary will be independently analyzed and compared to one another. The impact on change in exacerbation frequency and severity will be analyzed. Changes in spirometry, 6MWD, GOLD grade and class and BODE scores prior to and after 90 days of HNHF-O2 will be analyzed.

This is a pilot study in which the primary outcome is to determine the feasibility of using high-flow nasal oxygen in patients with COPD who have been recently discharged from the hospital with a COPD exacerbation. As such it is not an efficacy trial and is powered based on the ability to detect safety issues or unforeseen problems. The sample size has been estimated based on the method described by Viechtbauer, et.al.⁷

The safety issue we have identified is the need to withdraw therapy because HNHF-O2 is not tolerated by the subject.

The formula for this calculation is based on the probability of observing at least one of these events:

$$P(x > 0) = 1 - (1 - \pi)^n \text{ where}$$

x = the number of events that occur across the total number of participants
and

π = the probability that the event will occur.

Solving for n yields:

$$n = \frac{\ln(1 - \gamma)}{\ln(1 - \pi)}$$

Where γ = the confidence threshold.

Using a 95% confidence threshold and 15% probability that an event (need to discontinue due to intolerance) occurs the sample size required is:

Outpatient HNHF-O2 Protocol

Version 3.0

10/06/2017

$$n = \frac{\ln(1-0.95)}{\ln(1-0.1)} = 28.4 \text{ subjects.}$$

The number of subjects has been increased to 36 to accommodate screen failures and dropouts and to provide evaluable data on 30 subjects.

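### The sample-size section plans for 36 subjects to leave 30 evaluable, but the abstract, recruitment and accrual sections plan for thirty, which leaves no allowance for dropout

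*Combined protocol and SAP*

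**What the plan says.** Section 10(i), Data Management, computes a base size of 28.4 from the probability of seeing at least one event, and then states: "The number of subjects has been increased to 36 to accommodate screen failures and dropouts and to provide evaluable data on 30 subjects". The event is defined just before the formula: "The safety issue we have identified is the need to withdraw therapy because HNHF-O2 is not tolerated by the subject".

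Three other sections give a different number. Section 1 (Abstract): "This is an open-labeled pilot study of thirty patients". Section 10(a) (Recruitment Methods), on the number to be enrolled, begins "Thirty patients hospitalized for acute exacerbation of COPD". Section 10(c) (Local Number of Subjects): "Thirty subjects will be accrued locally for this study", followed by "We expect few screen failures". Section 10(d) marks the study-wide number as not applicable, so no other site supplies the difference.

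The schedule in section 10(g) places consent at the screening visit and baseline tests at Visit 1a. The device comes later: "After the 2-week run-in period the patient will be scheduled to return to initiate HFNC with oxygen therapy". The number expected to start the device is not given. Neither is a screen-failure rate, a dropout rate, a replacement rule or a definition of evaluable.

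**The concern.** The two numbers serve different purposes and cannot both be the enrolment target. The six subjects between 36 and 30 are the plan's only allowance for losses, and section 10(i) says that they cover dropouts as well as screen failures. If recruitment stops at thirty enrolled, the allowance for dropouts after enrolment disappears while 30 evaluable is still promised.

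Two things are at stake. Staff cannot tell from the document whether to stop at thirty or at 36. And the before/after comparisons at Day 90 (blood gases, spirometry, walk distance, BODE) would rest on fewer subjects than the sample-size section states.

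**Working it through.** **Inputs.** From section 10(i): confidence threshold 0.95; event probability 15% in the text but 0.1 in the printed formula; inflated size 36; evaluable target 30. From sections 1, 10(a) and 10(c): thirty. The dropout rate is an assumption. I use 10% and 15%, borrowed from the plan's two intolerance figures only because the documents offer nothing else. Evaluable is read as having Day 90 data, and losses are treated as independent.

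**Step 1: the plan's own figure.** n = ln(1 − 0.95)/ln(1 − 0.1) = 28.43, so the printed 28.4 reproduces and rounds up to 29. With 0.15 the formula gives 18.43, or 19. That mismatch is a separate matter; here it only explains why two rates are carried through.

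**Step 2: the loss implied by 36.** (36 − 30)/36 = 16.7%, screen failures and dropouts combined.

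**Step 3: what each starting number yields.** Expected number with Day 90 data = n(1 − d). The chance of reaching 30 is a binomial tail, which for n = 30 is (1 − d)^30.

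| Number at risk of dropout | d = 10% | d = 15% |
|---|---|---|
| 30: expected | 30 × 0.90 = 27.0 | 30 × 0.85 = 25.5 |
| 30: chance that all 30 have data | 0.90^30 = 4.2% | 0.85^30 = 0.8% |
| 36: expected | 36 × 0.90 = 32.4 | 36 × 0.85 = 30.6 |
| 36: chance of at least 30 | 93.7% | 71.0% |
| 33 (if 3 of 36 fail screening): expected | 33 × 0.90 = 29.7 | 33 × 0.85 = 28.05 |

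So 36 is roughly consistent with 30 evaluable at these rates, and thirty is not.

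**Step 4: precision at Day 90.** The half-width of a 95% CI for a mean change is proportional to t(0.975, n − 1)/√n. This is 0.373 at n = 30 and 0.396 at n = 27, or 5.9% wider. At n = 26 it is 8.2% wider and at n = 25 10.5% wider; these two bracket 25.5.

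**Step 5: the event calculation.** The chance of at least one event is 1 − (1 − π)^n. With all thirty counted it is 1 − 0.90^30 = 95.8%, or 1 − 0.85^30 = 99.2%. Both exceed the 95% threshold, because thirty is already above the 29 required at 10%.

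**The case against.** The best defence is that 36 counts consented subjects and thirty counts those who start the device. Consent precedes baseline, and the device starts only after a two-week run-in, so subjects can be lost to screening or drop out before any treatment. That would account for both kinds of loss named in section 10(i). The reading is possible, but it is nowhere stated, and it strains sections 10(a) and 10(c), which speak of enrolment and accrual. It also leaves no allowance for subjects who drop out during the 90 days on the device.

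A second defence is that evaluable is undefined. A subject who stops for intolerance has supplied the tolerance outcome, and section 10(m) retains data collected up to withdrawal. For the tolerance endpoint, then, thirty starters can yield thirty usable subjects. This stands, and it confines the shortfall to measures that need a Day 90 value. It does not remove the mismatch, since section 10(i) itself sets dropouts against evaluable data.

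Third, the assumed losses equal the intolerance figures, while those same subjects count as events for tolerance. That is fair. The 27.0 and 25.5 describe the before/after measures only, and some who stop the device may still attend at Day 90.

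**Conclusion.** The inconsistency is real and should be fixed. As written, 36 and thirty cannot both hold, and thirty enrolled gives 30 with Day 90 data only if nobody drops out. At an assumed 10% or 15% loss the expected number is 27.0 or 25.5. The cost is a modest loss of precision in a descriptive pilot, and the event calculation is barely affected.

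Three stronger conclusions might be inferred, and the documents do not support them.

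- *That the trial falls below its 95% detection threshold.* With 28 subjects counted, detection at 10% would be 94.8%, so two losses would suffice. This requires leaving lost subjects out of the count, and section 10(i) defines the event count over all participants.
- *That the tolerance denominator excludes withdrawn subjects.* No sentence excludes them. Section 10(i) analyses tolerance trends across all patients, section 10(l) calls for review of those who stop the device, and section 10(m) keeps their data. The text points toward counting them.
- *That hours of use will be overstated by averaging only those still on the device.* No section plans this. The clinic-visit assessments in section 10(g) list "Hours of daily use of HNHF-O2 therapy", so a subject who stops the device but stays in the study can have zero hours recorded. No rule covers the days after a subject leaves the study, but zero hours after a stop is only one defensible summary, so its absence is not an error.

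**What to change.** 1. Use one set of numbers in sections 1, 10(a), 10(c) and 10(i). Either state that 36 are consented or enrolled to yield 30 with Day 90 data, or keep thirty accrued and restate the expected number with Day 90 data as below 30.
2. Say whether 36 and thirty each count consented subjects, enrolled subjects or device starters, and give the loss rate assumed.
3. As a safeguard, state that tolerance is reported over all subjects who start HNHF-O2, with every withdrawal for intolerance counted as an event. Reserve the term evaluable for the before/after measures.
4. Optionally, show hours of use over all starters alongside hours while on the device. This is a clarification, not a correction.

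The cost is wording in four sections and, if not already captured, the date and reason of each device stop. Choosing 36 means up to six more subjects than thirty. Choosing thirty means accepting, and stating, fewer than 30 with Day 90 data.
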